1.2.1. Precautions and Risks Associated with BDTX-189

Dose-limiting toxicities have included reversible Grade 3 ALT/AST increases, Grade 3 diarrhea (lasting >24 hours), Grade 3 dehydration, and intolerable Grade 2 and Grade 3 nausea and vomiting. Gastrointestinal disorders increased in frequency and severity with increasing doses. A total of 72% of the patients across all dose levels experienced treatment-related gastrointestinal TEAEs, of which 19% were Grade 3 severity. A total of 14% experienced a drug-related skin disorder TEAE. No patients have experienced a treatment-related TEAE of Grade 4 or 5 severity. Further details are described in the IB.

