4.3.2. Dose-limiting Toxicity

Toxicity will be assessed using the NCI [CTCAE Version 5.0](#) unless otherwise specified.

A toxicity will be considered dose-limiting (unless clearly attributable to an extraneous cause, such as underlying disease) if it occurs during the first cycle (21 days) of treatment with BDTX-189. Dose-limiting toxicities (DLTs) will be defined as follows:

- Any death not clearly due to the underlying disease or extraneous causes.
- Hematologic toxicity
 - Grade 4 neutropenia or thrombocytopenia for >7 days or febrile neutropenia.
 - Grade 3 thrombocytopenia associated with bleeding or requiring a platelet transfusion.
 - Grade ≥ 4 anemia.
- Non-hematologic toxicity of \geq Grade 3 (at any time during treatment) that, in the judgment of the Investigator, is dose-limiting except for:
 - Grade 3 fatigue lasting <1 week.
 - Grade 3 nausea, vomiting, or diarrhea lasting <5 days without adequate supportive care.

- Grade 3 nausea, vomiting, or diarrhea lasting <24 hours with adequate supportive care.
- The following non-hematologic laboratory abnormalities:
 - Baseline Grade ≤ 1 ALT or AST: any drug -related Grade ≥ 3 abnormality of ALT and/or AST or increase in ALT or AST $>3 \times$ ULN with a concurrent increase in total bilirubin $>2 \times$ ULN (per Hy's Law).
 - Baseline Grade ≥ 2 ALT or AST due to liver metastases: any drug-related ALT and/or AST $>2 \times$ baseline or $\geq 10 \times$ ULN.
- Dose reduction during Cycle 1 due to an AE related to BDTX-189.
- Delay of starting Cycle 2 for >2 weeks if due to an AE related to BDTX-189.
- Interruption of BDTX-189 dosing for more than 7 days during Cycle 1, if due to a drug-related AE.

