Total bilirubin $\geq 2.0 \times$ ULN and ALT or AST $\geq 3.0 \times$ ULN (Potential Hy's Law) See Section 8.2.4 for further details	
1st occurrence: Omit dose and repeat tests 2-3 times a week until all abnormal lab results resolved to \leq Grade 1 (or baseline), then \downarrow 1 dose level
 
2nd occurrence: Omit dose and discontinue patient from study treatment

Diarrhea	
Grade 1	Maintain dose level. Stop treatment with concomitant medications that may cause diarrhea (e.g., laxatives). Administration of standard doses of loperamide should be initiated.
Grade 2	Optimize anti-diarrheal medication. Temporarily interrupt BDTX-189 until resolved to Grade ≤ 1 . Resume same dose level unless associated with complicating signs/symptoms, in which case consider \downarrow 1 dose level.
Grade 3	Optimize anti-diarrheal medication. Temporarily interrupt BDTX-189 until resolved to Grade ≤ 1 . If the severity lasts <24 hours during Cycle 1, resume at the same dose level. If the severity persists for >24 hours or resumes, then \downarrow 1 dose level.
Grade 4	Discontinue patient from study treatment
Skin rash	
Grade 1	Maintain dose level. Consider initiation of topical emollients, antihistamines in the case of pruritus, and/or topical (mild strength) corticosteroid creams
Grade 2	Maintain dose level at first occurrence and monitor rash closely. Initiate rash treatment if not already done. If rash worsen or reoccurs within 14 days, interrupt BDTX-189 until resolved to Grade ≤ 1 , then \downarrow 1 dose level.
Grade 3	At first occurrence, interrupt BDTX-189 administration and apply topical emollients, antihistamines, and/or high strength corticosteroid creams until it resolves to \leq Grade 1, then the study drug can be reinstated at current dose level. At second occurrence, interrupt BDTX-189 administration until resolved to Grade ≤ 1 , then \downarrow 1 dose level.
Grade 4	Study drug administration will be discontinued. Schedule dermatologist evaluation
Prolonged QTc interval	

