Grade 3-4	Permanently discontinue BDTX-189. Closely monitor LVEF until resolution or for up to 16 weeks.
All other BDTX-189 treatment-related adverse events	
Grade 1 or 2 (except fatigue, alopecia, and laboratory abnormalities not requiring medical intervention)	Maintain dose level if the event is Grade 1 or non-persistent Grade 2. If the event is persistent Grade 2 not responding to a specific therapy, consider $\downarrow 1$ dose level.
Grade 3	Omit dose until resolved to \leq Grade 1 or baseline level, then $\downarrow 1$ dose level
Grade 4	Discontinue patient from study treatment

Abbreviations: ALT = alanine aminotransferase; AST = aspartate aminotransferase; ECG = electrocardiogram; LLN = lower limit of normal; LVEF = left ventricular ejection fraction; NCI CTCAE = National Cancer Institute Common Terminology Criteria for Adverse Events; QTcF = QT interval corrected according to Fridericia's formula; ULN = upper limit of normal. Note: After the MTD was exceeded for the QD and BID schedules in fasted state, subsequent cohorts were evaluated non-fasted (fed). For Dose reduction levels refer to [Table 7](#).

Intrapatient dose-escalation during Part A may be considered in the absence of \geq Grade 2 toxicities related to BDTX-189 in the following circumstance: After a new higher dose level has been determined to be tolerated ($\leq 30\%$ DLTs), any patients remaining on study and being treated with a lower dose of BDTX-189 may, at the discretion of the Investigator and with agreement of the Sponsor, be offered treatment at the new higher tolerated dose once that dose level evaluation has been cleared. During the Safety Expansion and Part B, re-escalation of BDTX-189 following dose reduction due to toxicities may be considered following discussion and approval of Sponsor's Medical Monitor.

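### Following Table 8 for related short Grade 3 nausea, vomiting or fatigue triggers the Cycle 1 dose-reduction DLT bullet, which undoes the Section 4.3.2 exceptions

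*Combined protocol and SAP*

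**What the plan says.** Section 4.3.2 lists non-hematologic toxicity of Grade 3 or higher as a DLT if the investigator judges it dose-limiting, and carves out three kinds of event:

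- Tiredness of limited length: "Grade 3 fatigue lasting <1 week"
- Gastrointestinal events where support was lacking: "Grade 3 nausea, vomiting, or diarrhea lasting <5 days without adequate supportive care"
- The same gastrointestinal events where support was given, with a much shorter limit: "Grade 3 nausea, vomiting, or diarrhea lasting <24 hours with adequate supportive care"

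The carve-outs sit inside that one bullet. Later bullets in the same list stand alone, and one of them is "Dose reduction during Cycle 1 due to an AE related to BDTX-189". It has no exception of its own.

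Section 4.3.5 sends the reader to Table 8 for the criteria on interruption, reduction and discontinuation. Table 8 has rows for creatinine, bilirubin, AST/ALT, bilirubin combined with AST/ALT, diarrhea, rash, QTc and LVEF, and a last block headed "All other BDTX-189 treatment-related adverse events". In that block the Grade 3 line holds dosing until the event is at most "Grade 1 or baseline level, then" lowers the dose by one level. It sets no condition on duration. Fatigue is mentioned only as an exclusion in the Grade 1 or 2 line. The Grade 3 diarrhea row differs: "If the severity lasts <24 hours during Cycle 1, resume at the same dose level".

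**The concern.** The DLT definition says that certain brief Grade 3 events should not count. The dosing table tells the site to respond to those events, when drug-related, with an action that does count. Two sites facing the same short episode of Grade 3 vomiting could record different DLT outcomes, depending on whether each followed Table 8.

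The DLT rate is the Part A primary estimand (Section 9.2). The DLT count drives the Table 6 actions and the isotonic estimate of the MTD (Section 4.3.1). The events are not rare types for this drug: Section 1.1.7 gives any-grade rates of 47.7% for nausea, 44.6% for vomiting and 29.2% for fatigue. The point also looks forward. A 400 mg BID cohort was enrolling, and Section 4.3.1 applies elimination boundaries to toxicity in up to 48 expansion patients.

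**Working it through.** **1. The two sections side by side, for a related event in Cycle 1.**

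| Grade 3 event | Section 4.3.2 exception | Table 8 action | Result if restarted in Cycle 1 |
|---|---|---|---|
| Nausea or vomiting, <24 h with adequate care | Yes | Catch-all: down one level | DLT through the reduction bullet |
| Nausea or vomiting, <5 days without adequate care | Yes | Catch-all: down one level | DLT through the reduction bullet |
| Fatigue, <1 week | Yes | Catch-all: down one level | DLT through the reduction bullet |
| Diarrhea, <24 h, not recurring | Yes | Same dose | Not a DLT; aligned |
| Diarrhea, past 24 h but <5 days without adequate care | Yes | Down one level | DLT through the reduction bullet |

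The exceptions still work for unrelated events, when the restart falls after Day 21, and when the investigator departs from Table 8.

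**2. Reproducing Table 6.** The target is φ = 0.3 (Section 4.3.1). The documents do not state the other design constants, so I assume the usual BOIN defaults, φ1 = 0.6φ = 0.18 and φ2 = 1.4φ = 0.42.

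- λe = ln[(1−φ1)/(1−φ)] / ln[φ(1−φ1)/(φ1(1−φ))] = ln(0.82/0.70) / ln(0.246/0.126) = 0.2365
- λd = ln[(1−φ)/(1−φ2)] / ln[φ2(1−φ)/(φ(1−φ2))] = ln(0.70/0.58) / ln(0.294/0.174) = 0.3585
- Escalate if DLTs ≤ floor(λe·n). De-escalate if DLTs ≥ ceil(λd·n). From n = 3, eliminate if P(p > 0.3 | data) > 0.95 under a Beta(1,1) prior.

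All 15 columns of Table 6 are reproduced.

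**3. What one patient does to the action (illustration only).**

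| n | DLTs with the patient counted | DLTs with the exception honored |
|---|---|---|
| 3 | 1: stay | 0: escalate |
| 6 | 2: stay | 1: escalate |
| 6 | 3: de-escalate | 2: stay |

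**4. What a systematic excess would do.** The documents give no rate for such events, so this is an assumed range. Take a true DLT rate of 0.20 and n = 6, with X binomial. Then P(escalate) = P(X ≤ 1) and P(de-escalate) = P(X ≥ 3).

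| Points added by excepted events | P(escalate) | P(de-escalate) |
|---|---|---|
| 0 | 0.655 | 0.099 |
| 5 | 0.534 | 0.169 |
| 10 | 0.420 | 0.256 |
| 15 | 0.319 | 0.353 |

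**5. Can the reported DLTs be bounded?** Section 1.1.7 gives 2 + 2 DLT patients (1200 and 1000 mg QD) and 3 + 3 (800 and 600 mg BID), 10 in all. Six patients had a diarrhea DLT, five vomiting and four nausea, with overlap. Section 1.2.1 describes the DLTs as including "Grade 3 diarrhea (lasting >24 hours), Grade 3 dehydration, and intolerable Grade 2 and Grade 3 nausea and vomiting". No duration is given for nausea or vomiting, no supportive-care status for diarrhea, and no qualifying criterion for any patient. The number affected cannot be derived.

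**The case against.** The strongest reply is that this is a deliberate and cautious design. The reduction, Cycle 2 delay and over-7-day interruption bullets are separate triggers: a brief Grade 3 event is not a DLT by itself, but one that forces a lower dose is. Table 8 is also titled as guidelines and worded as recommendations, and the Safety Review Committee looks at all safety data, not only DLT counts.

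Part of this stands. The error runs in the safe direction, and a site may choose not to follow Table 8. But the separate-trigger reading works only if the reduction is a clinical choice. Here the catch-all directs it for every related Grade 3 event without its own row, and states no same-dose option. Unrelated events need the exceptions least, because Section 4.3.2 already sets aside toxicity clearly due to another cause. Following both rules therefore leaves the exceptions little to do. The diarrhea row, with its own Cycle 1 24-hour rule, suggests alignment was intended and not carried over to nausea and vomiting, which Section 4.3.2 treats together with diarrhea.

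Two stronger readings are tempting and not supported:

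- **At most 4 of the 10 DLT patients are in question (10 − 6 = 4).** This is not a bound. Diarrhea past 24 hours can still be excepted if it lasted under 5 days without adequate supportive care. In the other direction, Section 4.3.5 bars reduction below the initial starting dose and Section 4.1 says BID began at 800 mg BID, so it is unclear whether any BID patient could have qualified through a reduction.
- **The Grade 2 nausea and vomiting DLTs show the conflict at work.** Grade 2 events were never excepted. They imply only that the reduction, delay or interruption bullet was used for some patient.

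**Conclusion.** The conflict is in the text and should be fixed. It applies when the event is drug-related, the site follows Table 8, a lower level is available, and dosing restarts within Cycle 1. Its direction is over-counting of DLTs, hence toward a lower MTD. Its size in this trial is unknown: one patient can move a Table 6 action, but the documents do not show that any did.

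A reader might infer that the selected dose is too low because of this. The documents do not support that. No DLT was reported in the escalation cohorts at 800 mg QD or below, so the count at that dose is not inflated, and fatigue is not among the reported DLTs. Nor were the decisions above 800 mg QD plainly mechanical: 6 and 7 patients were treated at 1200 and 1000 mg QD, and if all were evaluable Table 6 gives stay for 2 DLTs.

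What remains open is the criterion behind the nausea and vomiting DLTs and the longer diarrhea DLTs, and the rule for patients still to come. For the 400 mg BID escalation cohort the reach is uncertain. The Section 4.3.5 bar may rule out a reduction there, although Table 5 lists a lower projected BID start. For expansion patients, Table 7 does supply lower levels.

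**What to change.** 1. Extend the Grade 3 diarrhea rule in Table 8 to nausea and vomiting. Optimize anti-emetics and interrupt until Grade 1 or lower. In Cycle 1, if the event lasted under 24 hours with adequate supportive care, restart at the same dose. If it lasted longer or recurs, reduce one level.
2. For the longer exceptions (fatigue under 1 week; nausea, vomiting or diarrhea under 5 days without adequate supportive care), have the clinical team choose either a same-dose restart in Table 8 or removal of the exception from Section 4.3.2. The diarrhea row is no precedent for a full-dose restart after nearly 5 days of vomiting or a week of fatigue, so this is a clinical decision.
3. Record for every DLT, past and future, which Section 4.3.2 criterion was met.
4. Show the Table 6 action and the isotonic MTD with and without any patient who qualified solely through a reduction for an excepted event.

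The cost is a short amendment to Table 8 (and to Section 4.3.2 if an exception is dropped), one added data item, and a listing with a sensitivity display. The downside is that some patients resume the tested dose after Grade 3 nausea or vomiting of under 24 hours, as is already allowed for diarrhea.

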4.3.2.1. Determination of DLT-evaluable Population

The patient population used for determination of DLTs will consist of patients who have met the minimum safety evaluation requirements of the study or who have experienced a DLT.

Minimum safety requirements will be met if, during Cycle 1 of treatment, the patient receives at least 75% of planned total doses of BDTX-189 (i.e., 16 of 21 QD doses or 32 of 42 BID doses unless due to dose hold guidelines provided in [Table 8](#)) and is observed for at least 21 days following the first dose of BDTX-189. Patients receiving less than 75% of the planned doses of BDTX-189 due to drug-related AEs that are not considered a DLT may still be evaluable for determination of DLTs.

If a patient withdraws from treatment during Cycle 1 due to any reason other than DLT and does not meet the minimum requirements for inclusion in the DLT-evaluable population described above, an additional patient may be enrolled to ensure an adequate number of evaluable patients. Patients being evaluated for Food Effect will not be part of the DLT-evaluable population per the BOIN design parameters; however, the safety information from these patients will be considered when making decisions about Dose Escalation/de-escalation and determination of the RP2D.

4.3.3. Maximum-tolerated Dose

The BOIN design will be used to find the MTD in this study. The target toxicity rate for the MTD will be $\phi = 0.3$ and the maximum sample size will be 36 evaluable patients for the QD schedule and 24 patients for the BID schedule, should that be explored. Please see Section [4.3.1](#) and [Table 6](#) for complete details.

4.3.4. Safety Expansion after Determination of the Maximum-Tolerated Dose

As described in Section [1.1.7](#), the MTD and preliminary RP2D is 800 mg for the QD schedule. Once the Safety Expansion opens for enrollment, up to 48 additional patients (including patients for PK evaluation of a smaller and reformulated tablet [see below]) will be enrolled at the MTD or a lower dose for either the QD and/or the BID schedule to further characterize the safety, PK, and efficacy profile. The MTD will be considered the recommended dose unless there is a lower dose that provides adequate exposure and biologic activity with more favorable tolerability.

A smaller and reformulated 200 mg tablet will be introduced and may be supplied to some patients during the Safety Expansion of Part A; these tablets will be available to all patients enrolling on Part B. A minimum of 12 patients from selected study sites may undergo PK evaluation on C1D1 and C1D15 (see Section 5.6) during the Safety Expansion period and/or Part B.

Should the PK parameters from these smaller and reformulated tablets be consistent with data from the larger tablets, additional PK evaluation can be performed in newly enrolled patients on C1D1 and C1D15 and/or by switching patients from the larger tablets to the smaller and reformulated 200 mg tablets to further characterize the PK. The latter subset of patients in Part A who initiated treatment with the larger 200 mg tablet may be switched to the smaller and reformulated 200 mg tablet at the beginning of the subsequent cycle. Detailed PK sampling will be collected on Day 15 of that subsequent cycle according to [Table 10](#), to provide additional exposure data.

4.3.5. Dose Modifications

If toxicity occurs, the toxicity will be graded using the NCI [CTCAE Version 5.0](#), and appropriate supportive care treatment will be administered to decrease the signs and symptoms thereof. Dose adjustments will be based on the organ system exhibiting the greatest degree of toxicity.

Specific criteria for interruption, re-initiation, dose reduction, and/or discontinuation of BDTX-189 are listed in [Table 8](#). All interruptions or modifications must be recorded on the AE and drug administration eCRFs. Appropriate clinical experts must be consulted as deemed necessary.

The Investigator will evaluate which AEs are attributed to the study drug and adjust the dose of the drug as recommended below. All dose modifications must be based on the worst preceding toxicity ([CTCAE Version 5.0](#)).

Patients whose treatment is delayed due to AEs may continue treatment if the AE resolves within 21 days of onset. Any patient who requires a treatment interruption of more than 21 days due to AEs will be discontinued from study treatment unless the Investigator and the Medical Monitor agree that continued treatment at the appropriate dose is in the best interest of the patient.

A maximum of 2 dose reductions are allowed in this study. [Table 7](#) outlines acceptable dose reductions for patients in the Safety Expansion of Part A or Part B, who are enrolling after the implementation of Amendment 3. Once the dose of BDTX-189 has been reduced because of toxicity, all subsequent cycles must be administered at that lower dose level unless further dose reduction is required. The patient will be withdrawn from study treatment if further toxicity meeting the requirement for dose reduction occurs. Dose reduction below the initial starting dose levels for QD and BID in Part A, respectively, is not allowed. Otherwise, the patient must be removed from treatment.

Recommended BDTX-189 dose modifications are presented in [Table 8](#).

Table 7 Dose Reduction Levels for BDTX-189 Administered Once or Twice Daily

Original dose	800 mg QD	400 mg BID
Dose level -1	600 mg QD	300 mg BID

Dose level -2	400 mg QD	200 mg BID
---------------	-----------	------------

Table 8 Dose Modification Guidelines for BDTX-189-related Adverse Events

Recommended Dose Modifications	
Worst toxicity NCI CTCAE v5.0 Grade (value)	Recommended dose modification any time during a cycle of therapy
Renal	
Serum creatinine	
≤1.5 × ULN	Maintain dose level
Grade 2 (>1.5 to 3 × ULN)	Omit dose until resolved to baseline, then 
 • If resolved ≤ 7 days, then maintain dose level • If resolved > 7 days, then ↓ 1 dose level
Grade 3 (>3.0 to 6.0 × ULN)	Discontinue patient from study treatment
Grade 4 (>6.0 × ULN)	Discontinue patient from study treatment
Hepatic	
Total bilirubin	
<1.5 × ULN	Maintain dose level
Grade 2 (>1.5 to 3 × ULN if baseline was normal; >1.5 to 3.0 × baseline if baseline was abnormal)	Omit dose until resolved to baseline, then 
 • If resolved ≤ 7 days, then maintain dose level • If resolved > 7 days, then ↓ 1 dose level
Grade 3 (>3.0 to 10.0 × ULN if baseline was normal; >3.0 to 10.0 × baseline if baseline was abnormal)	Omit dose until resolved to baseline, then 
 • If resolved ≤ 7 days, then ↓ 1 dose level • If resolved > 7 days and discontinue patient from study treatment
Grade 4 (>10.0 × ULN if baseline was normal; >10.0 × baseline if baseline was abnormal)	Discontinue patient from study treatment Note: If Grade 3 or 4 hyperbilirubinemia is due to the indirect (unconjugated) component only and hemolysis has been ruled out as the etiology as per institutional guidelines (e.g., review of peripheral blood smear and haptoglobin determination), then ↓ 1 dose level and continue treatment at the discretion of the Investigator
AST or ALT	
Grade 1 (>ULN to 3.0 × ULN if baseline was normal; >1.5 to 3.0 × baseline if baseline was abnormal)	Maintain dose level
Grade 2 (>3.0 to 5.0 × ULN if baseline was normal; >3.0 to 5.0 × baseline if baseline was abnormal)	Maintain dose level
Grade 3 (>5.0 to 20.0 × ULN if baseline was normal; >5.0 to 20.0 × baseline if baseline was abnormal)	Omit dose until resolved to ≤ Grade 1 (or ≤ Grade 2 if liver metastases present), then either maintain dose level (if Grade 3 lasted ≤ 7 days) or ↓ 1 dose level (if Grade 3 lasted > 7 days)
Grade 4 (>20.0 × ULN if baseline was normal; >20.0 × baseline if baseline was abnormal)	Discontinue patient from study treatment

Recommended Dose Modifications

Worst toxicity NCI CTCAE v5.0 Grade (value)	Recommended dose modification any time during a cycle of therapy
Combination of bilirubin and AST/ALT	
Total bilirubin $\geq 2.0 \times$ ULN and ALT or AST $\geq 3.0 \times$ ULN (Potential Hy's Law) See Section 8.2.4 for further details	
1st occurrence: Omit dose and repeat tests 2-3 times a week until all abnormal lab results resolved to \leq Grade 1 (or baseline), then \downarrow 1 dose level
 
2nd occurrence: Omit dose and discontinue patient from study treatment

Diarrhea	
Grade 1	Maintain dose level. Stop treatment with concomitant medications that may cause diarrhea (e.g., laxatives). Administration of standard doses of loperamide should be initiated.
Grade 2	Optimize anti-diarrheal medication. Temporarily interrupt BDTX-189 until resolved to Grade ≤ 1 . Resume same dose level unless associated with complicating signs/symptoms, in which case consider \downarrow 1 dose level.
Grade 3	Optimize anti-diarrheal medication. Temporarily interrupt BDTX-189 until resolved to Grade ≤ 1 . If the severity lasts <24 hours during Cycle 1, resume at the same dose level. If the severity persists for >24 hours or resumes, then \downarrow 1 dose level.
Grade 4	Discontinue patient from study treatment
Skin rash	
Grade 1	Maintain dose level. Consider initiation of topical emollients, antihistamines in the case of pruritus, and/or topical (mild strength) corticosteroid creams
Grade 2	Maintain dose level at first occurrence and monitor rash closely. Initiate rash treatment if not already done. If rash worsen or reoccurs within 14 days, interrupt BDTX-189 until resolved to Grade ≤ 1 , then \downarrow 1 dose level.
Grade 3	At first occurrence, interrupt BDTX-189 administration and apply topical emollients, antihistamines, and/or high strength corticosteroid creams until it resolves to \leq Grade 1, then the study drug can be reinstated at current dose level. At second occurrence, interrupt BDTX-189 administration until resolved to Grade ≤ 1 , then \downarrow 1 dose level.
Grade 4	Study drug administration will be discontinued. Schedule dermatologist evaluation
Prolonged QTc interval	
Grade 2 QTcF >480 msec and ≤ 500 msec	
 1. Repeat ECG in triplicate as soon as practical, no later than 7 days after the initial ECG. If the mean QTcF on repeat ECG triplicate is ≤ 500 msec and the patient is asymptomatic, then continue study drug at the same dose. Post-dose ECG must be monitored weekly in triplicate. 2. If the mean QTcF on repeat ECG triplicate is >480 and ≤ 500 msec, then consultation with cardiologist (must occur as soon as practical, no later than 7 days after the initial ECG). 3. If the cardiologist confirms a mean QTcF >480 and ≤ 500 msec is drug-related, then \downarrow 1 dose level.
Grade 3 QTcF >500 msec or QTcF increased by ≥ 60 msec from baseline	
 1. Repeat ECG in triplicate approximately 1 hour after the initial ECG 2. If the mean QTcF on repeat ECG triplicate is >500 msec or increased by ≥ 60 msec from baseline, then omit dose until consultation with cardiologist (must occur as soon as practical, no later than 7 days after

Recommended Dose Modifications	
Worst toxicity NCI CTCAE v5.0 Grade (value)	Recommended dose modification any time during a cycle of therapy
	
the initial ECG). ECG must be monitored in triplicate at the frequency selected at Investigator's discretion.
 
3. If the cardiologist confirms a mean QTcF >500 msec or increase by ≥ 60 msec from baseline is drug-related, then $\downarrow 1$ dose level. If second occurrence is attributed to BDTX-189, then discontinue patient from study treatment.

Left ventricular systolic dysfunction	
Asymptomatic absolute decrease of 10% – 19% in LVEF compared to baseline and the LVEF is below the Institution's LLN (e.g., a decrease from 60% to 48% is an absolute decrease of 12%)	
Interrupt BDTX-189 and repeat evaluation of LVEF within 2 weeks:
 
 • If LVEF recovers to $\geq 50\%$ or \geq LLN and 
 ◦ absolute decrease $\leq 10\%$ compared to baseline in 21 days, then maintain dose level ◦ absolute decrease $>10\%$ compared to baseline in 21 days, then $\downarrow 1$ dose level after approval of Medical Monitor. Monitor LVEF 2 weeks after resuming, every 4 weeks for 12 weeks and subsequently per protocol • If the LVEF does not recover in ≤ 21 days, permanently discontinue BDTX-189. Closely monitor LVEF until resolution or for up to 16 weeks.
Grade 3-4	Permanently discontinue BDTX-189. Closely monitor LVEF until resolution or for up to 16 weeks.
All other BDTX-189 treatment-related adverse events	
Grade 1 or 2 (except fatigue, alopecia, and laboratory abnormalities not requiring medical intervention)	Maintain dose level if the event is Grade 1 or non-persistent Grade 2. If the event is persistent Grade 2 not responding to a specific therapy, consider $\downarrow 1$ dose level.
Grade 3	Omit dose until resolved to \leq Grade 1 or baseline level, then $\downarrow 1$ dose level
Grade 4	Discontinue patient from study treatment

Abbreviations: ALT = alanine aminotransferase; AST = aspartate aminotransferase; ECG = electrocardiogram; LLN = lower limit of normal; LVEF = left ventricular ejection fraction; NCI CTCAE = National Cancer Institute Common Terminology Criteria for Adverse Events; QTcF = QT interval corrected according to Fridericia's formula; ULN = upper limit of normal. Note: After the MTD was exceeded for the QD and BID schedules in fasted state, subsequent cohorts were evaluated non-fasted (fed). For Dose reduction levels refer to [Table 7](#).

Intrapatient dose-escalation during Part A may be considered in the absence of \geq Grade 2 toxicities related to BDTX-189 in the following circumstance: After a new higher dose level has been determined to be tolerated ($\leq 30\%$ DLTs), any patients remaining on study and being treated with a lower dose of BDTX-189 may, at the discretion of the Investigator and with agreement of the Sponsor, be offered treatment at the new higher tolerated dose once that dose level evaluation has been cleared. During the Safety Expansion and Part B, re-escalation of BDTX-189 following dose reduction due to toxicities may be considered following discussion and approval of Sponsor's Medical Monitor.

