Patients in Part A who terminate participation in the study for any reason other than DLTs before completing Cycle 1 and patients who do not receive at least 75% of the planned doses of BDTX-189 in Cycle 1 for any reason other than DLT-related interruptions will be considered non-evaluable (NE) for DLTs, and additional patients may be enrolled to ensure an adequate number of DLT-evaluable patients. Additional patients may also be enrolled if there are patients who are deemed NE for food effect PK assessment.

Patients who experience a DLT but who, in the opinion of the Investigator, are deriving clinical benefit will be permitted to continue treatment with BDTX-189 at a lower dose that has been demonstrated to be well tolerated upon resolution of the DLT. In total approximately 128 patients will be enrolled in Part A.

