5.5. Early Patient Termination/Patient Withdrawal

Patients who discontinue treatment early due to PD, a DLT, or withdrawal will be asked to have all EOT safety evaluations performed as described in the protocol (see the Schedule of Assessments [[Table 1](#), [Table 2](#), and [Table 3](#)]). If a patient withdraws from treatment during Cycle 1 due to any reason other than a DLT and does not meet the minimum requirements for inclusion in the DLT-evaluable population described in Section [4.3.3](#), an additional patient may be enrolled to ensure an adequate number of evaluable patients.

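### In Part A Cycle 1, Table 8 keeps the full dose through an ALT/AST rise that Section 4.3.2 counts as a DLT in patients with liver metastases and a raised baseline, and no text says Section 4.1 takes precedence

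*Combined protocol and SAP*

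**What the plan says.** **DLT definition (Section 4.3.2).** A toxicity counts "if it occurs during the first cycle (21 days) of treatment". For patients with baseline Grade 2 or higher "ALT or AST due to liver metastases: any drug-related ALT and/or AST" above 2 × baseline, or at 10 × ULN or more, is a DLT. For baseline Grade 1 or lower, any drug-related Grade 3 or higher ALT/AST is a DLT, with no allowance for short duration.

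**After a DLT (Section 4.1).** A Part A patient whom the investigator judges to be benefiting may "continue treatment with BDTX-189 at a lower dose that has been demonstrated to be well tolerated upon resolution of the DLT". No other route to continued dosing after a DLT is described. Section 5.5 mentions "Patients who discontinue treatment early due to PD, a DLT, or withdrawal" when it asks for end-of-treatment evaluations.

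**Dose modification (Section 4.3.5, Table 8).** The text states: "Specific criteria for interruption, re-initiation, dose reduction, and/or discontinuation of BDTX-189 are listed in" Table 8. When the baseline was abnormal, the table grades ALT/AST in multiples of baseline. Grade 1 (above 1.5 to 3.0 ×) and Grade 2 (above "3.0 to 5.0 × baseline if baseline was abnormal") both keep the current dose. The first hold for an isolated rise is the Grade 3 row, above 5.0 × baseline.

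**Eligibility (Section 3.2, criterion 1c).** With liver metastases, ALT/AST excludes a patient only at 5.0 × ULN or more, so a Grade 2 baseline (above 3 and below 5 × ULN) can be enrolled.

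**The concern.** For the same patient, laboratory value and cycle, one section declares the event dose-limiting and provides only for a lower dose after recovery, while the dosing table tells the site to carry on unchanged. A site working from Table 8 would keep giving the full dose through a protocol-defined DLT, in patients whose transaminases were already raised at entry.

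ALT/AST is a known toxicity of this drug. Section 1.2.1 lists reversible Grade 3 ALT/AST increases among the DLTs. Section 1.1.7 reports increased ALT in 23.1% of patients, and at Grade 3 or higher in 7.7%. The DLT rule was also still in use: the 400 mg BID cohort was enrolling (Section 1.1.7), and up to 48 Safety Expansion patients were to be monitored against the DLT elimination boundaries (Section 4.3.1).

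**Working it through.** The plan states no figure to reproduce. The check compares two rules over the eligible baselines.

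**Inputs**
- Eligible Grade 2 baseline *b*: above 3 and below 5 × ULN (Section 3.2, criterion 1c, with the Grade 2 limits in Table 8).
- DLT if the value exceeds 2*b* or is at least 10 × ULN (Section 4.3.2).
- Table 8 keeps the dose up to 5*b* and omits it above 5*b*.
- Bilirubin below 2 × ULN. Otherwise the combined bilirubin and transaminase row of Table 8 applies, which omits the dose and then reduces it one level.

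**Which DLT limb acts first.** For every *b* below 5, 2*b* is below 10, so the 2 × baseline limb is reached before 10 × ULN.

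**Overlap = above 2*b*, up to 5*b***

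| Baseline (× ULN) | DLT above, 2*b* (× ULN) | Dose kept up to, 5*b* (× ULN) |
|---|---|---|
| 3.1 | 6.2 | 15.5 |
| 4.0 | 8.0 | 20.0 |
| 4.9 | 9.8 | 24.5 |

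**Values at *b* = 4.0**
- 2.0 × baseline = 8.0 × ULN: not a DLT.
- 2.1 × baseline = 8.4 × ULN: DLT; Table 8 Grade 1, dose kept.
- 4.0 × baseline = 16 × ULN: DLT; Table 8 Grade 2, dose kept.
- 5.1 × baseline = 20.4 × ULN: DLT; Table 8 Grade 3, dose omitted.

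For baselines above 4 × ULN the top of the band passes 20 × ULN, the level above which Table 8 discontinues a patient with a normal baseline.

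**Does Table 8 apply in Cycle 1?** Yes, on three grounds.
- Its column heading covers any time in a cycle, and Section 4.3.5 makes no exception for DLTs.
- Section 4.3.2.1 counts Cycle 1 doses as "16 of 21 QD doses or 32 of 42 BID doses unless due to dose hold guidelines provided in" Table 8.
- Its Grade 3 diarrhea row refers to Cycle 1 and uses a 24-hour limit like the one in Section 4.3.2. Diarrhea was aligned with the DLT rule; ALT/AST was not.

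**Smaller form of the same gap.** For baseline Grade 1 or lower, a drug-related Grade 3 ALT/AST is a DLT whatever its duration. Table 8 does hold the drug, until Grade 1 or lower (or up to "Grade 2 if liver metastases present), then either maintain dose level (if Grade 3 lasted" 7 days or less). A short episode therefore resumes at the same dose, where Section 4.1 provides a lower one.

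**The resolution level.** On the abnormal-baseline scale, the Grade 2 allowance in that row reaches 5 × baseline: 20 × ULN when *b* = 4, against a DLT line of 8 × ULN. It cannot serve as the resolution level for this subgroup.

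**The case against.** The best reply is that Section 4.1 already handles this. It is the specific rule for a Part A patient who has had a DLT. Table 8 is a general adverse-event table headed as guidelines and recommendations, so a site that follows Section 4.1 departs from a recommendation rather than breaking a prohibition. Other protections exist: Section 3.3 stops treatment for laboratory abnormalities attributed to drug toxicity, Section 4.3.5 calls for expert consultation as needed, and the Safety Review Committee reviews Cycle 1 laboratory data (Section 10.3.1).

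Much of this stands. Section 4.1 is the natural rule to govern, and a careful site would probably apply it. It would go too far to say that sites are left with no workable reading. But no text gives Section 4.1 precedence, Section 4.3.5 presents Table 8 as the specific criteria for holding and reducing, and the Section 3.3 clause sets no ALT/AST threshold.

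Three stronger inferences are tempting, and the documents do not support them.
- *The dose-finding is compromised.* DLTs are counted from Section 4.3.2, not from Table 8, so the BOIN decisions and the MTD do not depend on the Table 8 row. Part B does not use the DLT rule.
- *The exposure can be sized.* A rise first seen at the Day 8 chemistry leaves Days 8 to 21, that is 14 days, in Cycle 1. That bounds the further full dosing for one patient at a site that sets Section 4.1 aside. Neither it nor the number of BID or Safety Expansion places estimates how many patients are affected.
- *The reported ALT/AST DLTs were such cases.* Sections 1.1.7 and 1.2.1 do not give the baseline status of those patients.

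**Conclusion.** The conflict is in the text and holds for every eligible Grade 2 baseline: an isolated drug-related rise above 2 and up to 5 × baseline in Part A Cycle 1 is both a DLT and a reason to keep the dose. The scope is narrow. The share of patients with a Grade 2 or higher baseline is not given, so the number affected is unknown, and no case is reported. The point is a minor-to-moderate dosing-safety correction.

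The conclusion rests on two readings. First, the laboratory bullet in Section 4.3.2 is a DLT criterion, not one of the exceptions listed just before it; otherwise Hy's Law cases would be exempt, and the ALT/AST DLTs the protocol reports would not fit. Second, Section 4.1 permits only a lower dose after a DLT, because no other form of continuation is described.

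**What to change.** Add one note to Table 8, for example: *In Part A Cycle 1, if the event meets the DLT definition in Section 4.3.2, Section 4.1 governs regardless of the row below: interrupt BDTX-189 until the DLT resolves; a patient deriving clinical benefit may then resume only at a lower dose shown to be well tolerated.* This covers both the main conflict and the short Grade 3 case.

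For baseline Grade 2 or higher due to liver metastases, the note should define resolution as a return to no more than 2 × baseline and below 10 × ULN, or a stricter level of the sponsor's choosing. It should not borrow the Grade 2 allowance from the Grade 3 row.

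A separate hold at 2 × baseline in the ALT/AST rows is not needed. If one is added, it must be limited expressly to Part A Cycle 1. Without that limit it would bring a new and debatable hold into later cycles and into Part B (up to about 491 patients).

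The cost is a short addition to one table, with no new tests or patients. A few Part A patients would be held or reduced earlier than Table 8 alone requires.
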